The minimal risk of death has been related to plasmatic glucose levels of 89 mg/dl (4.94 mmol/l) (range 78 -101 mg/dl or 4.33-5.6 mmol/l), glucose levels between 60 to 80 mg/dl (3.33 to 4.44 mmol/l) had an OR of 1.06, and glucose levels between 100 to 200 mg/dl (5.55 to 11.10 mmol/l)

were associated with an odds ratio of 1.32 for in-hospital death. Interestingly, the relation of plasmatic glucose with mortality showed a “J” shape curve, suggesting that low or high blood glucose levels are both deleterious (5). In cardiac surgery patients and Acute Coronary Syndrome (ACS), the risk threshold begins with blood glucose levels as low as 140 mg/dl (7.77 mmol/l). Other authors mention this “J” shape curve in the relation between blood glucose levels and mortality (2, 3).

Mortality, length of in-hospital stay and acute kidney failure have been associated to hyperglycemia in different studies postoperatively (3, 6).

During acute inflammation, hyperglycemia decreases vasodilatory response and reduces the blood flow to the sites of infection (or inflammation), it also increases endothelial permeability and tissue edema, which can cause multisystem organ dysfunction (4). Hypoglycemia is one of the main limitations for the tight glycemic control. Frequency of hypoglycemia varied between 24.3 to 27.8 %, in the glucose-controlled patients, and between 72.2 to 75.6% in non-controlled patients(6).

Not only hyperglycemia causes damage, glycemic variability and hypoglycemia does too, and it seems to be worse than hyperglycemia itself.

Mean amplitude of glycemic excursions keeps and almost lineal relation ($r 0.86$) with the renal excretion of 8-iso prostaglandin $F_{2\alpha}$, a marker of oxidative stress (7). Hypoglycemia itself increases C-reactive protein and pro-inflammatory cytokines (TNF- α , interleukin-1 β , IL-6, and interleukin-8), markers of lipid peroxidation, ROS, and leukocytosis (3).

There is an apparent paradox: hyperglycemia increases the danger of death and morbidities in hospitalized patients, but the best treatment option – insulin – can be more dangerous itself, because of the hypoglycemia risk.

The recommended treatment of hospitalized patients with hyperglycemia is a combination of insulin analogs This is accomplished using insulin analogs with slow release rate (basal insulin) and other

ones with fast or very fast release rate (prandial insulin); the so-called basal bolus insulin regimen. As general rule point of care capillary glucose determinations are performed before meals, to adjust the dose of prandial insulin (8).

The incidence of cardiovascular events in T2D patients are a set of adverse outcomes of interest; drugs used for the treatment of T2D are required to probe that do not increase the risk of cardiovascular diseases (9).

The evaluation of DPP4 (dipeptidyl peptidase-4) inhibitors has provided variable evidence. Most of the studies have proved that the use of DPP4 inhibitors is safe, regarding cardiovascular outcomes(10, 11). The odds ratio for hospitalization for heart failure (HF) in iDPP4 users were 1.00 (95% CI 0.94 to 1.07), incident HF 1.01 (95% CI 0.92 to 1.11) recurrent HF 1.02 (95% CI 0.84 to 1.22). All-cause mortality was 6% lower in iDPP4 users ($p < 0.001$). Insulin users showed an excess of risk for any type of hospital admission (19%) and death (20%) ($p < 0.001$) (12).

Different studies in patients with acute coronary syndrome and high cardiovascular risk have shown a safe profile of linagliptin regarding cardiovascular and renal function (13-15).

Post-transplanted renal patients have a particularly high risk of hyperglycemia after renal transplantation (RT). Surgery procedures are related with elevation of blood glucose levels; as result of the trauma itself there is release of cytokines and stress response hormones that cause insulin resistance. In post transplanted patients, we must add the use of immunosuppressive therapy that worsens this insulin resistance effect. The incidence of hyperglycemia is common in these patients; for example, in post kidney transplanted patients the frequency reported is between 80 to 90 %. Sometimes, the patients were already diabetic previous to the transplant (but unaware); other times, they are actually new diabetes cases. Hyperglycemia in the perioperative period, independently if the patients continues with post-transplant diabetes mellitus (PTDM) or remits to

normoglycemia, has been related to increased graft rejection, infections or readmission to the hospital because of infection (16).

The recommended treatment of hyperglycemia in kidney transplanted patient is insulin analogs. There are several algorithms that had proven to be effective; but as the conditions of these patients can change rapidly (adjustment of the immunosuppressive drugs, changes in renal function or nutrition therapy), they require intensive blood glucose monitoring, effective communication among the health care team (nurses and physicians), flexible treatment algorithms, and training of the personal to understand and implement properly these algorithms. All these conditions create a very challenging environment for the adequate use of insulin analogs. The use of DPP4 inhibitors in the treatment of diabetic patients that had underwent kidney transplantation is increasing. There are, nevertheless, few studies that had assessed the efficacy and security of these drugs, in the setting of diabetic kidney transplanted patients (16).

Although they all are capable to lower glucose, they do not do so in the same proportion. In the study by Bae et al, they compared the hypoglycemic effect of three different DDP4 inhibitors (sitagliptin, vildagliptin and linagliptin) *in a population of renal transplanted diabetic patients*; it was found that the mean difference between the pre and post treatment glycated hemoglobin (HbA1c) were -0.53 for sitagliptin, -0.38 for vildagliptin and – 1.4 for linagliptin. In the same study, it was reported that the average cyclosporine blood levels in the pre and post treatment period changed +30.62 ng/mL in sitagliptin group, -24.22 ng/mL in vildagliptin group and -8.5 ng/mL in linagliptin group (17).

The goal of this work was to evaluate the effect of the combined treatment with insulin plus linagliptin in comparison with insulin alone on glucose control and hypoglycemia in post-transplanted renal patients who present hyperglycemia immediately after RT.

Material and methods

Study design and population

This was a retrospective comparative study performed in a single center between 2016 and 2018, included the data collected from 28 hospitalized post-renal transplanted patients that presented hyperglycemia (>140 mg/dl or 7.77 mmol/l) immediately after RT; 14 patients were treated with linagliptin 5mg daily plus a basal bolus insulin scheme prescribed by the Endocrinology group at the hospital, and 14 patients treated only with basal bolus insulin scheme were randomly selected from a list of patients treated during the same period of time and by the same Endocrinology group. Linagliptin dose was 5mg daily and the basal bolus insulin regimen was started and adjusted according to the international guidelines; in general, patients received a starting insulin dose of around 0.5 U/kg/day, given half as basal insulin (NPH or Glargine) once or twice daily and half as insulin lispro divided into three equal doses before meals. Insulin dose was adjusted daily to achieve the goal of fasting glucose between 80-140 mg/dl (4.44-7.77 mmol/l) or random glucose levels below 180 mg/dl (9.99 mmol/l). Correctional insulin dose was used before each meal, depending on the glucose measurements, starting at 1 unit for each 40mg above 140 mg/dl (7.77 mmol/l) of glucose. Glucose levels were monitored at fasting and before each meal, as well as at bedtime according to standard clinical practice. Data regarding fasting and preprandial glucose levels, hypoglycemia, renal function, and immunosuppression therapy were recorded from the patient's file during the first 5 days after RT; fasting glucose and renal function were also recorded at 1, 6 and 12 months after RT. Patients were included if they were between 18-65 years of age and presented fasting hyperglycemia (>140 mg/dl or 7.77 mmol/l) immediately after RT.

Ethical and Research committee at the Hospital approved the study protocol with the number CEI-49-18.

Fasting glucose was measured by dry chemistry with colomitetric method (Vitros 5600; Ortho Clinical Diagnostics), pre-lunch and pre-dinner glucose were measured by capillary method using and Accu-check glucometer. Hypoglycemia was defined when glucose levels were <70 mg/dl (3.88 mmol/l).

Main Outcomes were glucose levels during the first 5 days in hospital and after 6 and 12 months, insulin dose, frequency and severity of hypoglycemia, and renal function at 1, 6 and 12 months after RT.

Statistical analysis

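### The in-hospital window is counted from transplantation, with no first-dose day or baseline defined, so the qualifying glucose and other pre-dose readings can enter the outcome

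*Combined protocol and SAP*

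**What the plan says.** All of the design text is in Material and methods, Study design and population.

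- **Entry.** Patients were included if they "presented fasting hyperglycemia (>140 mg/dl or 7.77 mmol/l) immediately after RT".
- **Arms.** Groups are defined by treatment received: "14 patients were treated with linagliptin 5mg daily plus a basal bolus insulin scheme", against 14 patients on basal-bolus insulin alone, drawn at random from a list for the same period and the same clinical group.
- **Start of treatment.** The plan says "the basal bolus insulin regimen was started and adjusted according to the international guidelines". It gives no day or time, relative to transplantation, for the first insulin dose or the first linagliptin dose.
- **Recording window.** Fasting and preprandial glucose, hypoglycemia, renal function and immunosuppression were taken from the chart "during the first 5 days after RT".
- **Outcome window.** "Main Outcomes were glucose levels during the first 5 days in hospital and after 6 and 12 months". Insulin dose is also a main outcome, but no window is attached to it.

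The Statistical analysis section plans an unpaired t test between groups, a paired t test within groups and a chi-square test for proportions. It names no baseline and no covariate adjustment, and does not say whether the five days are averaged or tested one by one.

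**The concern.** Three clocks should agree in a comparison of this kind: when a patient qualifies, when the compared treatment starts, and when outcome counting begins. Here the first and third are tied to transplantation, and the second is not stated. Fasting glucose is both the entry variable and an outcome variable, and no rule keeps the entry value, or any other reading before the first dose, out of the outcome.

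Two consequences are possible. First, readings taken before a patient's first linagliptin dose carry no information about adding linagliptin, so including them in an average pulls the arms together. Second, if the regimens began on different days in the two arms, the arm that started later contributes more untreated readings, and a difference can appear with no drug effect. Treatment was not randomised and the planned tests are unadjusted, so nothing later in the analysis corrects for either. With 28 patients there is little precision to spare.

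**Working it through.** **No figure to reproduce.** The documents give no sample-size calculation, effect size or SD. What follows is an illustration on stated assumptions.

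**Inputs from the plan:** 14 patients per arm; a five-day window; unpaired t test; p < 0.05. Readings are monitored at fasting, before meals and at bedtime. Counting fasting, pre-lunch and pre-dinner gives 3 × 5 = 15 readings; adding bedtime gives 4 × 5 = 20; fasting values alone give 5.

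**Assumptions:** two-sided test; five-day means compared; effect constant once on treatment; SD of the mean unchanged; the same number of pre-dose readings in both arms. The reference effect is 1.10 SD, chosen because it gives 80% power at 14 v 14 when every reading is on treatment.

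**Step 1: dilution.** If a share s of the averaged readings is pre-dose, the expected difference is 1.10 × (1 − s) SD. Power comes from the noncentral t distribution with 14 + 14 − 2 = 26 degrees of freedom and noncentrality d × √(14/2), where d is the diluted difference.

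| Pre-dose content | s | d (SD) | Power |
|---|---|---|---|
| none | 0 | 1.10 | 80% |
| 1 of 20 readings | 0.05 | 1.10 × 0.95 = 1.045 | 76% |
| 1 of 15 readings | 0.067 | 1.10 × 0.933 = 1.027 | 74% |
| 1 of 5 fasting values, or 1 of 5 days | 0.20 | 1.10 × 0.80 = 0.88 | 61% |
| 2 of 5 days | 0.40 | 1.10 × 0.60 = 0.66 | 39% |
| 3 of 5 days | 0.60 | 1.10 × 0.40 = 0.44 | 20% |

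The normal approximation gives 83%, 64%, 42% and 21% for 0, 1, 2 and 3 pre-dose days, so the pattern does not depend on the method.

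**Step 2: bias from unequal starts.** With no true drug effect, the shift in the difference of five-day means is (difference in start days) × (pre-treatment minus on-treatment glucose) / 5. For an assumed gap of 20 to 80 mg/dl:

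- one day apart: 1 × 20/5 = 4 to 1 × 80/5 = 16 mg/dl;
- two days apart: 2 × 20/5 = 8 to 2 × 80/5 = 32 mg/dl.

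The sign depends on which arm started later, which the documents do not say.

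**Step 3: reach.** If each day is tested separately, only the pre-dose days are affected. The 1-, 6- and 12-month measurements are barely touched by a shift of a few days in the origin.

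**The case against.** The strongest reply is that the five days describe what was abstracted from the chart, not which readings enter the comparison. The planned paired test needs a reference time point, and an early reading may be that baseline. The qualifying value could precede the first recorded day. Treatment may have begun the same day, leaving little more than one pre-dose reading, and some patients may already have been on insulin when they qualified. Both arms share the entry rule, the period and the clinical group. The transplant anchor also has merit: the introduction says these patients' condition can change quickly, and counting from surgery compares the arms on the same postoperative day.

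Much of this stands. A reader might infer that pre-treatment readings were analysed as outcome and that the contrast was diluted or biased. The documents do not show that, because start days and analysed readings are not given. A reader might also infer that insulin dose is measured over days 1-5, but insulin dose is absent from the list of items recorded in that window.

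The reply does not remove the point. It relies on choices the plan never states. A same-day start does not fully protect the fasting outcome either: if the qualifying value is one of five fasting values, a fifth of that average is pre-dose. The value of comparing on the same postoperative day is a reason to match controls on that day, not a reason to leave the start of exposure undefined.

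**Conclusion.** The point holds as a defect of definition with real consequences for the analysis. Time zero and baseline are not specified, and the rules as written allow the qualifying glucose and other pre-dose readings into an unadjusted, non-randomised comparison. The two descriptions of the window, one from transplantation and one from hospital days, need to be aligned, and neither refers to the start of treatment.

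The size is unknown. It runs from nearly nothing (a same-day start with the qualifying value set aside, or daily tests read only after the first dose) to a serious loss if linagliptin began several days after surgery. The power and mg/dl figures above show scale only; the 1.10 SD effect, the glucose gaps and the start days are all assumed. The point concerns in-hospital glucose and hypoglycemia; the power figures apply to mean glucose only. It should be corrected, but it does not by itself invalidate the study.

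**What to change.** 1. Abstract the dates of the first linagliptin dose and the first basal-bolus insulin dose from the same charts, and report the post-transplant day of each by arm.
2. Start each linagliptin patient's outcome window at the first linagliptin dose. Start each control's at the same post-transplant day as a matched linagliptin patient, with similar time since insulin start. Do not use first linagliptin dose in one arm and first insulin dose in the other: if linagliptin was added later, the arms would be compared at different points of recovery and insulin titration.
3. Use the qualifying fasting glucose and other earlier readings only as baseline.
4. For glucose, replace the unadjusted t test with a model adjusted for that baseline, such as ANCOVA, and state whether the five days are averaged or analysed by day.
5. Use one description of the window throughout, state the window for insulin dose, and keep the days-from-transplant analysis as a sensitivity analysis.

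The cost is one or two extra dates per chart for 28 patients, and slightly fewer outcome readings for late starters. If the dates show that everyone started on the same day, reporting that settles most of the question; the qualifying value still needs to be kept as baseline.

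### The insulin-alone controls are not screened for whether they could have received linagliptin, so patients unsuitable for the drug can enter only the control group

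*Combined protocol and SAP*

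**What the plan says.** Under Study design and population, the work is described as follows: "This was a retrospective comparative study performed in a single center between 2016 and 2018". It "included the data collected from 28 hospitalized post-renal transplanted patients that presented hyperglycemia", 14 per group.

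- **Linagliptin group:** "14 patients were treated with linagliptin 5mg daily plus a basal bolus insulin scheme prescribed by the Endocrinology group at the hospital". Membership follows from treatment received. The reason for prescribing linagliptin to these patients is not given.
- **Control group:** 14 patients on the basal bolus scheme alone, "randomly selected from a list of patients treated during the same period of time and by the same Endocrinology group".
- **Entry rule:** "Patients were included if they were between 18-65 years of age and presented fasting hyperglycemia", with a threshold of 140 mg/dl. No exclusion criteria are listed. Diabetes type, prior insulin use and suitability for linagliptin are not mentioned.

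Insulin dose and the frequency and severity of hypoglycemia are among the main outcomes. The Statistical analysis section compares groups by unpaired t test and chi-square test, with no covariate or stratum.

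On who these patients are, the background says only: "Sometimes, the patients were already diabetic previous to the transplant (but unaware); other times, they are actually new diabetes cases".

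**The concern.** The question is what adding linagliptin to insulin does, so the fair comparison is among patients who could have had either treatment. Here the two groups pass through different gates. Everyone in the linagliptin group was judged suitable for the drug by the team, because they received it. Nobody in the control group had to meet that test.

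A patient the team would have treated with insulin only can enter one arm and not the other. Random sampling from the list does not help: it reproduces the list's composition, including any non-candidates. Adjusting for starting glucose would not fully repair it either, because such patients may have no counterpart in the linagliptin group. That makes this a matter of restriction at entry, separate from a general request for matching or covariate adjustment.

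With 14 controls, each patient is about 7% of the group (1/14), so a few such patients could visibly move a main outcome without any drug effect.

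**Working it through.** The plan gives no event rate, standard deviation, effect size or sample-size calculation, so there is no figure to reproduce. The following illustrates sensitivity.

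**Inputs from the plan:** 14 per group; chi-square for proportions; significance at p < 0.05. Sidedness is not stated; I take it as two-sided.

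**Assumed inputs:** hypoglycemia counted as patients with at least one event over the first 5 days; risk p0 in patients eligible for either regimen; risk p1 in non-candidates; k non-candidates among the 14 controls; no drug effect.

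**Step 1. Shift in the control rate** = (k/14) × (p1 − p0).

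With p0 = 20% and p1 = 60%:
- k = 1: 1/14 × 40 = 2.9 points
- k = 2: 2/14 × 40 = 5.7 points
- k = 4: 4/14 × 40 = 11.4 points

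With p0 = 20% and p1 = 40%:
- k = 2: 2/14 × 20 = 2.9 points
- k = 4: 4/14 × 20 = 5.7 points

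**Step 2. Chance of a significant result favoring linagliptin when the drug does nothing.** This is an exact enumeration of all outcome pairs at 14 vs 14, using chi-square without continuity correction.

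| p0 | p1 | k = 0 | k = 2 | k = 4 |
|---|---|---|---|---|
| 20% | 60% | 2.3% | 4.9% | 9.4% |
| 20% | 40% | 2.3% | 3.5% | 5.1% |

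**Step 3. Wider range.** For p0 of 10% to 30% and p1 of 40% to 80%, the shift runs from 0.7 points (k = 1: 1/14 × 10) to 20.0 points (k = 4: 4/14 × 70). At k = 4 the false-favorable chance runs from 3.7% to 22.3%. At k = 0 the shift is zero throughout.

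**Step 4. Insulin dose.** The shift in the control mean is (k/14) × gap, where the gap is the difference in requirement between non-candidates and other controls. For an assumed gap of ±0.2 U/kg/day, k = 1, 2 or 4 moves the mean by ±0.014, ±0.029 or ±0.057 U/kg/day. For scale, "in general, patients received a starting insulin dose of around 0.5 U/kg/day". The sign is entirely that of the assumed gap.

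**Step 5. Precision.** The standardized difference detectable with 80% power is (1.960 + 0.842) × √(2/14) = 1.06 SD. The study can resolve only large differences, and a bias of the sizes above could not be recognized from the outcome data themselves.

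**The case against.** A reader might infer that the control group did contain patients with type 1 diabetes, and that hypoglycemia and insulin dose are therefore both biased toward linagliptin. The documents do not support that.

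- **No such patient is shown.** Type 1 diabetes is never mentioned and the list's composition is not given. The background discusses this drug class in connection with type 2 diabetes, but it does not state who could receive linagliptin at this hospital. That a type 1 patient would have been passed over is an inference.
- **The direction for insulin dose is open.** The background describes the target population as insulin resistant from surgery and immunosuppression. Insulin-deficient patients could need more than these patients or less. Every patient in both groups received insulin, so needing insulin is not the same as needing a higher dose.
- **The net direction is open.** Since the reason for prescribing is unstated, patients who were harder to control may have been given linagliptin, which would push the other way.
- **Entry is narrower than age and glucose.** Patients also had to be hospitalized renal-transplant recipients on basal bolus insulin. Controls received that scheme alone, so other glucose-lowering agents are already ruled out in that arm.
- **Inability to take tablets is a weak example.** Insulin doses and glucose checks were tied to meals, so patients were generally eating.
- **The rates are assumed.** Even at 60% risk, 2 non-candidates add only about 0.8 of an expected patient with an event (2 × 0.40).

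All of this stands, and it limits the claim about direction and size. It does not remove the asymmetry: one group is filtered by the prescriber's judgment, the other is not, and nothing planned would reveal the difference. Swapping controls after the fact also carries its own risk if outcomes are visible, so the remedy must guard against that.

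**Conclusion.** The point holds as a gap in comparator selection. The documents leave open that patients unsuitable for linagliptin are in the control group, and they exclude this neither by an entry rule nor by analysis or planned reporting.

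The size is unknown and may be zero. Under the main assumptions (20% and 60% risk, 2 to 4 of 14 controls affected), the control hypoglycemia rate is raised by 5.7 to 11.4 points, and the chance of a false finding for linagliptin goes from 2.3% to between 4.9% and 9.4%. The shift halves if the non-candidate risk is 40%.

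A bias in hypoglycemia favoring linagliptin is plausible, provided non-candidates have the higher risk. For insulin dose, and for the net effect of all selection, no direction can be stated.

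**What to change.** 1. Add one eligibility rule for the comparison and apply it to both groups from chart data at the start of treatment: the patient could have received either regimen. Record diabetes type and ability to take oral medication for everyone. In the linagliptin group, also require no other non-insulin glucose-lowering drug; the definition of the controls already covers this for them.
2. Have the screen done by someone who does not see glucose, hypoglycemia or insulin-dose outcomes. Then draw controls at random from the screened list, or replace those who fail by a further random draw from it.
3. If the controls are fixed or the screened list is too short, keep them and add a sensitivity analysis excluding non-candidates.
4. State why linagliptin was prescribed in those who received it. Report diabetes type, pre-transplant diabetes and prior insulin use by group.

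The cost is a chart screen, a shorter list of potential controls (its length is not given) and results that apply to a slightly narrower population. If the screen finds no non-candidates, one sentence saying so settles the matter.
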